Re-screening	If a participant fails the initial screening and is considered as a Screen Failure, he/she can be invited once for a new Screening visit after medical judgment and as specified by the protocol
Remote	Describes any trial activities performed at a location that is not the investigative site where the investigator will conduct the trial, but is for example a home or another appropriate location
Screen Failure	A participant who did not meet one or more criteria that were required for participation in the study
Source Data/Document	Source data refers to the initial record, document, or primary location from where data comes. The data source can be a database, a dataset, a spreadsheet or even hard-coded data, such as paper or eSource
Start of the clinical trial	The start of the clinical trial is defined as the signature of the informed consent by the first participant
Study treatment	Any drug or combination of drugs or intervention administered to the study participants as part of the required study procedures; includes investigational drug(s), control(s) or background therapy
Study treatment discontinuation	When the participant permanently stops taking any of the study drug(s) prior to the defined study treatment completion date (if any) for any reason; may or may not also be the point/time of study discontinuation
Tele-visit	Procedures or communications conducted using technology such as telephone or videoconference, whereby the participant is not at the investigative site where the investigator will conduct the trial.
Treatment arm/group	A treatment arm/group defines the dose and regimen or the combination, and may consist of 1 or more cohorts.
Variable (or endpoint)	The variable (or endpoint) to be obtained for each participant that is required to address the clinical question. The specification of the variable might include whether the participant experiences an intercurrent event.

Withdrawal of study consent (WoC) / Opposition to use of data /biological samples Withdrawal of consent from the study occurs when the participant explicitly requests to stop use of their data and biological samples (opposition to use data and biological samples) AND no longer wishes to receive study treatment, AND does not agree to further protocol required assessments. This request should be in writing (depending on local regulations) and recorded in the source documentation.

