Potential adverse events from Nitazoxanide therapy: Nitazoxanide (Alinia[®]) will be administered to all participants with Cryptosporidium positive stool and/or clinical symptoms on Day 21. Nitazoxanide may be administered earlier to participants with persistent diarrhea on or after Day 10 to resolve diarrheal illness and minimize the risk of shedding or recurrent disease. To avoid unnecessary medication, participants without oocyst shedding at any time after Day 3 and without any diarrhea between Day 1 and Day 21 and without household contacts with diarrhea between Day 10 and Day 21 will not receive nitazoxanide. Nitazoxanide may also be administered as part of "rescue medication" to treat severe diarrheal illness before Day 10 (see Section 6.2.3). The most common adverse reactions in >2% of patients were abdominal pain, headache, chromaturia and nausea. In placebo-controlled clinical trials using the recommended dose of nitazoxanide, the rates of occurrence of these events did not differ significantly from those of the placebo. In controlled trials of patients age 12 years and older who received nitazoxanide for the treatment of diarrhea caused by Giardia lamblia or C. parvum, less than 1% of patients discontinued therapy because of an adverse event (Romark 2017). In the unlikely event that symptoms persist, the participant will, at the discretion of the Investigator, obtain additional diagnostic work-up and subsequent therapy (potentially including a second course of nitazoxanide) as appropriate (see Section 6.2.3).

The risks to participants in this trial may be minimized by compliance with the eligibility criteria and study procedures, as well as close monitoring. Refer to the Investigator's Brochure.

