6.1.2 Additional study treatments

Participants may receive nitazoxanide (see Section 6.2.3).

Table 6-2 Additional Study Treatment

Drug	Pharmaceutical	Route of	Supply Type
(Name and Strength)	Dosage Form	Administration	
Nitazoxanide 500 mg	Tablet	Oral use	Bottle

Nitazoxanide to be provided by clinical site

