For AEs that are not contained in the "Toxicity Grading Scale for Healthy Adult and Adolescent Volunteers Enrolled in Preventive Vaccine Clinical Trials (2007)", the following categorization will be used:

- Mild: usually transient in nature and generally not interfering with normal activities
- Moderate: sufficiently discomforting to interfere with normal activities
- Severe: prevents normal activities
- 2. The AE relationship (causality) to the study treatment will be assessed for all AEs recorded during treatment and follow-up by the investigator. The criteria for assessing the AE relationship to the study treatment are listed below:
 - a. Related There is reasonable possibility that the study treatment caused the AE. Reasonable possibility means that there is evidence to suggest a causal relationship between the study treatment and the AE.
 - b. Not related There is no reasonable possibility that the administration of the study treatment caused the event.
- 3. The AE duration (start and end dates) or if the event is ongoing, an outcome of not recovered/not resolved must be reported
- 4. Whether the AE constitutes an SAE (see Section 10.1.2 for the SAE definition)
- 5. Its outcome (i.e. recovery status or whether it was fatal)

AEs Follow-up

All adverse events must be treated appropriately. Conditions that were already present at the time of informed consent should be recorded in medical history of the participant.

Once an adverse event is detected, assessment must be made at each visit (or more frequently, if necessary) of any changes in severity, the suspected relationship to the interventions required to treat it, and the outcome. AEs must be followed, in person or by phone call as appropriate, until resolution or until judged to be permanent (i.e. unresolved at the EOS).

Abnormal laboratory values or test results constitute adverse events only if they fulfill at least one of the following criteria:

- they induce clinical signs or symptoms
- they are considered clinically significant
- they require therapy

Clinically significant abnormal laboratory values or test results must be identified through a review of values outside of normal ranges/clinically notable ranges, significant changes from baseline or the previous visit, or values which are considered to be non-typical in participants with the underlying disease.

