12.5.2 Safety endpoints

For all safety analyses, the safety set will be used. All listings and tables will be presented by treatment group.

Safety summaries (tables, figures) include data from Day 1 until the EOS with the exception of Baseline data which will also be summarized where appropriate (e.g. change from baseline summaries). In addition, a separate summary for death including on-treatment and post treatment deaths will be provided.

Adverse events

The number (and percentage) of participants with adverse events will be summarized in the following ways:

- by Primary system organ class and preferred term
- by Primary system organ class and preferred term and maximum severity

Separate summaries will be provided for ABO809 related AEs, SAEs, AESIs and deaths.

A participant with multiple AEs within a primary system organ class is only counted once towards the total of the primary system organ class.

Vital signs

All vital signs data will be listed by treatment group, participant, and visit/time and if ranges are available, abnormalities (and relevant orthostatic changes) will be flagged. Summary statistics will be provided by treatment and visit/time.

ECG findings

For ECG parameters, summary statistics for baseline value, actual assessment values, and change from baseline values will be presented by time of measurement. All ECG data will be listed; notably abnormal values will be flagged, and the overall interpretation of abnormality will be presented.

Clinical laboratory evaluations

Clinical laboratory data will include chemistry, hematology and urinalysis results up to EOS.

All laboratory values will be converted into International System of Units (SI) units. If grades are not defined by the Toxicity Grading Scale for Healthy Adult and Adolescent Volunteers Enrolled in Preventive Vaccine Clinical Trials (2007), results will be graded by the low/normal/high classifications based on laboratory normal ranges. Continuous laboratory data will be summarized by presenting summary statistics of raw data and change from baseline values (means, medians, standard deviations, ranges) by time point.

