2.1.1 General definitions

Study treatment: ABO809, $3x10^6$ *C. parvum* oocysts(CE)/3 mL as concentration for oral suspension. There will be no control drug used in this study. Additional study treatment is nitazoxanide 500 mg as tablet for oral use, which will be used as rescue medication on Day 21 and may be administered earlier based on clinical findings. Both are referred to as study treatment and rescue medication in the document, respectively.

The treatment group name alone (pooled analyses) and in addition to cohort number will be used in statistical analyses and outputs. The following abbreviated treatment groups will be used as the headers in the CSR outputs:

- ABO809 1x10⁴ CE cohort X
- ABO809 1x10⁶ CE cohort Y, if applicable
- ABO809 1x10^x CE cohort Z, if applicable (e.g. alternative dose)

Baseline: The last measurement made prior to administration of the first dose of study treatment. Note this may include measurements taken on the day before single dose administration (e.g. lab tests, ECG, vital signs, etc.).

Study day: Study day will be calculated with respect to the first dose of study treatment. The first day of administration of study treatment (first dose) is defined as Day 1. Day -1 will be the day before Day 1. There is no Day 0 designated in this study.

For assessments collected on or after Day 1, study day = date of assessment - date of first dose of study treatment + 1.

For assessments collected prior to Day 1, study day = date of assessment - date of first dose of study treatment.

Date of administration of study treatment: the day of administration of study treatment (ABO809 dose), is defined as Day 1.

Inpatient Follow-Up period: All participants, whether or not they are symptomatic, will be domiciled at the study site until completion of Day 10 assessments and then discharged if diarrheal symptoms have been resolved for ≥24 hours. Participants who experience symptoms

will remain domiciled for the duration of the diarrheal illness up to Day 21. If a participant experiences diarrhea after Day 10 (after the participant has been discharged from the study site), the participant may be readmitted, at the discretion of the Investigator, to remain domiciled until the cessation of symptoms or Day 21, whichever is earlier.

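### The term study treatment sometimes includes nitazoxanide and sometimes does not, so nitazoxanide reactions may be counted in the ABO809-related adverse event tables

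*Protocol*

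**What the plan says.** **Causality.** For adverse events up to Day 56, Protocol 10.1.1 states: "The AE relationship (causality) to the study treatment will be assessed for all AEs recorded during treatment and follow-up by the investigator". The answer is related or not related.

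**What study treatment means.** The Protocol glossary defines it as "Any drug or combination of drugs or intervention administered to the study participants as part of the required study procedures" and adds that it "includes investigational drug(s), control(s) or background therapy". Section 6.1.2, which sits under the heading for study treatment, lists nitazoxanide in "Table 6-2 Additional Study Treatment". SAP 2.1.1 separates the two products, naming ABO809 first and nitazoxanide second: "Both are referred to as study treatment and rescue medication in the document, respectively".

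**Tables.** Protocol 12.5.2 states: "Separate summaries will be provided for ABO809 related AEs, SAEs, AESIs and deaths". SAP 2.6.1 repeats this and also plans a summary of events related to study treatment. Safety summaries cover Day 1 to end of study (Protocol 12.5.2) and are presented by treatment group (SAP 2.6), meaning ABO809 dose. Neither document divides them at the start of nitazoxanide.

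**Nitazoxanide.** Every participant who becomes infected is to receive it on Day 21, or earlier under stated conditions (Protocol 4.1 and 6.2.3). Protocol 4.5 gives its reactions: "The most common adverse reactions in >2% of patients were abdominal pain, headache, chromaturia and nausea".

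**The concern.** A secondary objective is the safety and tolerability of ABO809 itself. With no control arm, attribution rests on the investigator's causality judgement and on timing. If that judgement can refer to either of two products, and the tables do not show which events began after the second was started, then a table labelled as ABO809-related may include reactions to nitazoxanide. These results are meant to support use of the infection model in later studies, so the safety profile should be that of the inoculum.

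The same loose term appears in the dosing-hold criteria of Protocol 9.1.4. The first criterion names ABO809; the next one refers to study treatment.

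**Working it through.** The plan gives no figure to reproduce here. The check compares definitions and table layout, with a short count of who is exposed.

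**1. The uses of the term, side by side**

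| Place | Meaning |
|---|---|
| Protocol glossary, study treatment | Broad: covers a drug that the procedures require |
| Protocol 6.1.2, Table 6-2 | Broad: nitazoxanide listed as additional study treatment |
| Protocol 6.7.2, Table 6-4 | Broad: nitazoxanide appears in the study treatment schedule, labelled as rescue |
| Protocol 10.1.5, Table 10-1 | Broad: the section on study treatment errors gives capture guidance for nitazoxanide |
| Protocol 9.1 and 9.1.1 | Narrow: ABO809, a single dose |
| Protocol 12.1 | Narrow: ABO809 is called treatment |
| SAP 2.1.1 | Narrow: ABO809 is study treatment, nitazoxanide is rescue medication |

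**2. What follows for one event.** Take a reaction that the investigator attributes to nitazoxanide. An investigator using the narrow meaning records it as not related. One using the glossary meaning may record it as related. The SAP would then read the second record as related to ABO809. Its definition governs how the data are tabulated; it cannot change what the site meant when it answered.

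**3. Whether the tables would reveal it.** SAP 2.4.3 and 2.5.3 make allowance for rescue medication in the infection profiles, stool data, durations and Kaplan-Meier analyses. SAP 2.6 has no counterpart for adverse events, laboratory values or ECGs.

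**4. Whether the event term would reveal it.** Only in part. Abdominal pain, headache and nausea are listed reactions to nitazoxanide (Protocol 4.5) and also symptoms linked to cryptosporidiosis (Protocol 1.1 for abdominal pain and headache; Table 2-1 and the Table 8-1 footnote on signs and symptoms for nausea). Chromaturia is not among the listed infection symptoms, so it would stand out.

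**5. How many participants take both products.** Inputs: expected infection rate 90 to 100 per cent (Protocol 1.2); 30 to about 60 participants (Protocol 3). Exposed = N × infection rate.

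- N = 30: 0.90 × 30 = 27 to 1.00 × 30 = 30.
- N = 60: 0.90 × 60 = 54 to 1.00 × 60 = 60.
- At 80 per cent, the lower end of the infection criterion in Protocol 6.5.1, N = 30 gives 0.80 × 30 = 24.

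**6. Laboratory and ECG timing.** Table 8-1 schedules these after dosing on Days 10 and 28. Day 28, one of the two time points, falls after the planned Day 21 course.

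**The case against.** The strongest reply is that the Protocol often does keep the two products apart. Its glossary has separate entries for additional treatment and for other treatment, the latter covering rescue therapy. Nitazoxanide is handled in Sections 6.2 and 6.2.3 as rescue medication and is captured on the concomitant medication page. Several places also name ABO809 outright: the calls up to Day 56 (Protocol 4.1, SAP 2.1.1), the first hold criterion in 9.1.4, SAE reporting in 10.1.3, and events of special interest after end of study in 10.1.1.1. Section 10.1.1 also mentions the suspected relationship to interventions, though without criteria or a planned table. The case report form is not among the documents, so a single causality field is inferred from the Protocol's wording.

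This stands, and it rules out several stronger readings:

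- **A reader might infer that nitazoxanide reactions will be reported as ABO809-related, or that causality is judged only against the broad term.** The documents support neither. The outcome depends on which meaning the investigator uses.
- **A reader might treat Days 21 to 56, 36 of 56 days or 64 per cent, as nitazoxanide exposure.** The course lasts 3 days, so calendar time after Day 21 is not time at risk from the drug.
- **A reader might add one or two caused events to a row, 1/30 to 2/30 or about 3 to 7 percentage points.** Protocol 4.5 says the listed rates were not significantly different from placebo, so the documents give no excess rate to apply.
- **A reader might conclude that the events can never be separated.** Adverse event start dates and nitazoxanide records are already collected and allow a before-and-after split. Infection symptoms also go under one diagnosis (10.1.1), so a symptom judged to have another cause would carry a different term.

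Some of the gap is covered already. SAP 2.3.4 allows optional tables of nitazoxanide use and of infection or symptoms after its last dose. The second hold criterion requires at least two similar severe events in a cohort, and dosing may resume after review.

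None of this settles what a recorded answer of related means between Day 1 and Day 56.

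**Conclusion.** The concern holds as an inconsistency and a risk. The Protocol and SAP do not give study treatment one meaning, causality up to Day 56 is described as one judgement against that term, and no adverse event summary is divided at the start of nitazoxanide. Nitazoxanide reactions may therefore enter the ABO809-related tables of an uncontrolled study in which about 27 to 30 of 30 participants are expected to take both products.

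The number of events affected is unknown and may be small. The conclusion assumes that some investigators could follow the glossary meaning, that the case report form matches the Protocol's wording, and that infection occurs at about the expected rate. The primary endpoint is not affected. This is a cheap improvement to the safety reporting.

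**What to change.** 1. Give study treatment one meaning across the Protocol glossary, Sections 6.1.2, 6.7.2, 9.1, 10.1.1, 10.1.5 and 12.1, and SAP 2.1.1.
2. In Protocol 10.1.1, record causality separately for ABO809 and for nitazoxanide.
3. In SAP 2.6.1, build the ABO809-related tables from the ABO809 item only.
4. In SAP 2.6.1, add an adverse event summary for two periods, before the first nitazoxanide dose and from that dose onward, using adverse event start dates and concomitant medication records.
5. In the laboratory and ECG outputs (SAP 2.6.3 and 2.6.4.1), flag Day 28 values by prior nitazoxanide use.
6. In Protocol 9.1.4, reconcile the adjacent hold criteria, which use two different terms. The choice of wording is for the sponsor.

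The cost is one extra field on the adverse event page, slightly more data entry at the site, one extra table and some wording changes. No visits or samples are added.

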10.1.1.1 Adverse events of special interest

All participants may report adverse events associated with *Cryptosporidium* infection as detailed in Section 4.5 Risks and benefits. The Investigator will report AESI and follow-up accordingly; these include:

- **Gastroenteritis in the absence of** *Cryptosporidium* **infection**: In the event of gastroenteritis in the absence of *Cryptosporidium* infection, the event will be considered an AESI. The Investigator will investigate other potential causes of diarrhea, including infectious diarrhea and manage participant's care according to local standards.
- Extraintestinal cryptosporidiosis: *Cryptosporidium* infection involving the biliary tract, lungs, liver, pancreas, or other organs will be considered AESI (also see Section 4.5 Risks and benefits).
- **Persistent or recurrent cryptosporidiosis:** Persistent clinical symptoms after administration of standard of care, or after initial resolution of *Cryptosporidium* oocysts in the stool and/or diarrheal symptoms, will be considered an AESI.
- **Persistent** *Cryptosporidium* **shedding:** Persistent detection of *Cryptosporidium* oocysts in stools after treatment with nitazoxanide will be considered an AESI. Participants with persistent shedding may be treated with combination therapy as detailed in Section 6.2.3.
- **Dehydration:** Moderate or severe dehydration, as defined below will be considered an AESI.
 - Mild: dry mucous membranes; diminished skin turgor; increased oral fluids are indicated
 - Moderate: IV fluids are indicated
 - Severe: hospitalization is indicated or it is considered to have life-threatening consequences; or an urgent intervention is indicated
- **Non-intestinal sequelae:** Development of new onset non-intestinal symptoms, including eye pain or joint pain, will be considered AESI.

If any AESIs are experienced after EOS (i.e. Post-Study Safety Follow-up calls at 6 and 12 months) in which the Investigator considers there is a reasonable possibility that ABO809 caused the event, the event will be recorded and reported following the same procedure as SAEs as described in Section 10.1.3. These AESIs will be captured in the Novartis safety database, included in an addendum to the CSR and reported to the competent authorities and relevant ethics committees as per national regulatory requirements in participating countries.

10.1.2 Serious adverse events

An SAE is defined as any adverse event [appearance of or worsening of any pre-existing] undesirable sign(s), symptom(s) or medical conditions(s) which meets any one of the following criteria:

- Fatal
- Life-threatening

A life-threatening SAE refers to a reaction in which the participant was at risk of death at the time of the reaction; it does not refer to a reaction that hypothetically might have caused death

if it were more severe (please refer to the ICH E2D (2004) Clinical Safety Data Management: Definitions and Standards for expedited reporting).

- Results in persistent or significant disability/incapacity
- Constitutes a congenital anomaly/birth defect
- Requires inpatient hospitalization or prolongation of existing hospitalization, unless hospitalization is for:
 - Social reasons and respite care in the absence of any deterioration in the participant's general condition
 - Treatment on an emergency outpatient basis for an event not fulfilling any of the definitions of a SAE given above and not resulting in hospital admission
 - Is medically significant, i.e. defined as an event that jeopardizes the participant or may require medical or surgical intervention to prevent one of the outcomes listed above

Medical and scientific judgment should be exercised in deciding whether other situations should be considered serious reactions, such as important medical events that might not be immediately life threatening or result in death or hospitalization but might jeopardize the participant or might require intervention to prevent one of the other outcomes listed above. Such events should be considered as "medically significant". Examples of such events are intensive treatment in an emergency room or at home for allergic bronchospasm, blood dyscrasias, convulsions that do not result in hospitalization or development of dependency or abuse (please refer to the ICH E2D (2004) Clinical Safety Data Management: Definitions and Standards for expedited r eporting).

All malignant neoplasms will be assessed as serious under "medically significant" if other seriousness criteria are not met.

Any suspected transmission via a medicinal product of an infectious agent is also considered a serious adverse reaction.

All reports of intentional misuse and abuse of ABO809 are also considered serious adverse event irrespective if a clinical event has occurred.

